5.9 Receiving, Storage, Dispensing and Return

5.9.1 Receipt of Drug Supplies

Study treatment supplies will be sent from Allergan, Inc. to each site specific Mayo Clinic Research Pharmacy.

Upon receipt of the study treatment supplies, an inventory will be performed and a drug receipt log filled out and signed by the person accepting the shipment. It is important that the designated study staff counts and verifies that the shipment contains all the items noted in the shipping invoice. Any discrepancies, damaged or unusable study drug in a given shipment (active drug or comparator) will be documented in the study files. The Principal Investigator will notify the study sponsor immediately of any discrepancies, damaged or unusable products.

5.9.2 Storage

Unopened vials of BOTOX® will be stored in a refrigerator (2° to 8°C) for up to 36 months for the 100 Units vial, in each site specific Mayo Clinic Research Pharmacy. The vials will not be used after the expiration date that appears on the vial. BOTOX® will be administered within 24 hours of reconstitution; during this period, reconstituted BOTOX® will be stored in a refrigerator (2° to 8°C). Reconstituted BOTOX® should be clear, colorless, and free of particulate matter.

All vials, including expired vials, or equipment used with the drug will be disposed of carefully, as is done with all medical waste.

5.9.3 Dispensing of Study Drug

Regular study drug reconciliation will be performed to document drug assigned, drug consumed, and drug remaining. This reconciliation will be logged on the drug reconciliation form, and signed and dated by the study team.

5.9.4 Return or Destruction of Study Drug

At the completion of the study, there will be a final reconciliation of drug shipped, drug consumed, and drug remaining. This reconciliation will be logged on the drug reconciliation form, signed and dated. Any discrepancies noted will be documented and investigated, prior to return or destruction of unused study drug. Drug destroyed on site will be documented in the study files.

6 Study Procedures

TABLE OF VISITS:

	Research activity	Subject activity
Preoperative evaluation/Surgical listing appointment	Study Coordinator (SC) reviews the study with eligible patients and obtains informed consent	Complete the BREAST-Q and Numeric Pain Intensity Scale
Surgery	Randomization by site specific research pharmacy and intra-operative injection of study drug by plastic surgeon	•
First post-operative visit: • Week 1- 2	SC facilitates completion of questionnaire and assesses for adverse events	Complete the BREAST-Q and Numeric Pain Intensity Scale
Subsequent Plastic Surgery Appointments/Expansion Visits • Beginning at week 2-3 and intervals thereafter as determined by the plastic surgeon	SC facilitates completion of questionnaire and assesses for adverse events	Complete the BREAST-Q and Numeric Pain Intensity Scale
• End of Study • The last plastic surgery appointment prior to removal of the TE, or the date of TE removal (whichever occurs last within the 4 month postoperative period)		

Tissue expander placement: The surgical procedure for submuscular placement of the tissue expander will be performed in the usual manner by each participating plastic surgeon.

BTX-A Injection Protocol: see Section 5.4

Outcome Assessment: The outcome measures selected to test our working hypothesis and answer our specific aim #1 are a numeric pain intensity scale (NPIS)⁷¹, and the Physical Well-Being scale of the BREAST-Q®: Reconstruction Module. These two measures will be administered to study participants at the pre-operative visit, the first postoperative visit (1-2 weeks), and subsequent Plastic Surgery appointments/expansion visits until the end of the study is reached.

7 Statistical Plan

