3.2 Primary Study Endpoints

The primary study endpoint is to determine the efficacy of a single intra-operative injection of BTX-A in the pectoralis major muscle on pain and physical well-being in women undergoing tissue expansions following mastectomy and immediate tissue expander breast reconstruction.

The outcome measures selected to test our working hypothesis and answer our specific aim #1 are a numeric pain intensity scale (NPIS)⁷¹, and the Physical Well-Being scale of the BREAST-Q®: Reconstruction Module. The NPIS is a reliable and valid tool that is widely used as a measure of pain intensity (See Appendix for complete scale). To assess physical well-being, we selected the 16-item Physical Well-Being scale from the BREAST-Q®: Reconstruction Module. The BREAST-Q® is a newly-developed and validated PRO measure designed to measure patients' perception of outcomes following breast surgery.⁷² The Reconstruction Module consists of scales in six domains related to satisfaction and QoL (See Appendix for complete scale). The Physical Well-Being scale has items that relate to issues surrounding chest and upper body symptoms, and how these impact on physical function and participation in activities before and after breast reconstruction. Study participants will answer how often they have experienced each symptom during the previous two-week period, using a 5-point Likert scale (1 – none of the time, 5 – very often). Answers from these questions will be combined to provide a total physical well-being score for each patient at each follow-up visit. Average scores for both study groups will be compared. These two measures will be administered at the pre-operative visit, the first postoperative visit (1-2weeks) and subsequent Plastic Surgery appointments/expansion visits until the end of study is reached. After much consideration, we have made the decision not to ask enrolled subjects to record the amount of oral analgesic medication taken

daily during the course of the study, as this method is often inaccurate due to missing data entries, and would therefore yield unreliable results. Furthermore, the randomization process in this study should ensure a random distribution of patients with different oral analgesics intakes. It was also felt that not recording the amount of oral analgesic medication would reduce the burden of study participants.

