3.3 Secondary Study Endpoints

Secondary study endpoints will include:

- 1) The initial percent volume expansion (defined as initial intraoperative fill volume divided by manufacturer recommended total tissue expander volume);
- 2) The rate of tissue expansion between the BTX-A group and the placebo group, with or without the use of ADM;
- 3) Rate of reconstructive failure (tissue expander removal for any reasons, such as infection or uncontrolled pain).

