7.2 Statistical Methods**Descriptive Statistics:**

Demographic and medical characteristics will be analyzed for all enrolled subjects. Descriptive statistics will be calculated for all baseline variables. Univariate descriptive statistics and frequency distributions will be calculated, as appropriate for all variables. Baseline values for demographic, clinical, and outcome variables (primary and secondary) will be tabulated separately for the treatment groups. These analyses will help identify whether the randomization was successful in equalizing distributions of these prognostic variables across treatment groups or if confounding variables need to be included as covariates in sensitivity analyses. Putative prognostic variables that will be investigated through these descriptive analyses include variables such as age, body mass index, smoking status, diabetes mellitus, coronary artery disease, hypertension, clinical breast cancer stage, mastectomy weight, initial percent volume expansion (defined as initial intraoperative fill volume divided by manufacturer recommended total tissue expander volume), sentinel lymph node biopsy, axillary dissection, adjuvant therapy factors (e.g., previous and postoperative chemotherapy and radiation), operative time, ADM use.

Handling of Missing Data

Handling of missing data will be done in a number of ways including complete-case analysis and multiple imputations via nearest neighbor, mean value, last value, and zero value carried forward

approaches. Multiple approaches are used so that the sensitivity of results to alteration in multiple imputational assumptions may be assessed.

Primary Hypotheses:

- Pain scores will be at least 25% less, in those who received BTX-A, during the immediate post-operative period compared to those who received saline injections
- Pain scores will be at least 25% less, in those who received BTX-A, during the period of tissue expansion, compared to those who received saline injections
- Physical Well-Being scores during tissue expansion will be higher in those who received BTX-A compared to those who received saline injections

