There are two primary outcomes: pain intensity measured by the NPIS, and physical well-being using the BREAST-Q®. The primary analysis will be performed during the post-operative period and during the expansion phase. Outcome variables will be summarized with frequency counts and percentages or means, standard deviations, medians, and ranges, as appropriate. The mean, median, standard deviation, and range of each variable and its change from baseline, measured on a continuous scale, will be presented by treatment and visit. Frequency tables will be provided for categorical variables by treatment and visit. Any differences among the study groups will be evaluated using two-sample t, Wilcoxon rank sum, Pearson's chi-square, or Fisher's exact tests.

Secondary Hypotheses:

- 1) There will be no difference in the initial percent volume expansion between groups (defined as initial intraoperative fill volume divided by manufacturer recommended total tissue expander volume);
- 2) The rate of tissue expansion will be higher in the BTX-A groups compared to the placebo group, with or without the use of ADM;
- 3) There will be no difference in the rate of reconstructive failure (tissue expander removal for reasons such as infection or uncontrolled pain).

The volume of tissue expansion anticipated and the rate of tissue expansion between the BTX-A groups and the placebo and control groups will be calculated both as an absolute value as well as a percentage. It is hypothesized that the use of BTX-A may increase the rate of tissue expansion, which may lead to fewer postoperative tissue expansion visits. This will allow measurement of effect size between the intervention and the placebo groups. Two-sample t and Wilcoxon rank sum tests will be used for the secondary analyses.

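### Expander removal for uncontrolled pain ends pain scoring, and the plan's rules for these women's later scores conflict, so the expansion-phase comparison can be biased either way

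*Combined protocol and SAP*

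**What the plan says.** Section 3.2 has both instruments completed before surgery, at the first postoperative visit and at "subsequent Plastic Surgery appointments/expansion visits until the end of study is reached". The Table of Visits in section 6 defines that end as "The last plastic surgery appointment prior to removal of the TE, or the date of TE removal"; the later of the two counts, up to four months after surgery. It does not distinguish planned exchange for the permanent implant from removal because the reconstruction failed.

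Section 3.3 lists as a secondary endpoint "Rate of reconstructive failure (tissue expander removal for any reasons, such as infection or uncontrolled pain"). Section 7.2 repeats that endpoint and names the primary ones: "There are two primary outcomes: pain intensity measured by the NPIS, and physical well-being using the BREAST-Q". On timing it says: "The primary analysis will be performed during the post-operative period and during the expansion phase". One of the primary hypotheses reads: "Pain scores will be at least 25% less, in those who received BTX-A, during the period of tissue expansion". No single visit or summary score is fixed.

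Four other provisions bear on a woman whose expander is removed early:

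- Section 4.4.2 keeps data collected before a withdrawal.
- Section 7.3 analyses all randomized subjects.
- Section 7.2 handles missing data by complete-case analysis and by nearest-neighbor, mean, last-value and zero-value imputation.
- Section 8.4 unblinds a subject who has an adverse event, classes her as a treatment failure and gives her the worst score on every outcome.

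Section 8.4 does not mention expander removal, and section 7 does not mention the section 8.4 rule.

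**The concern.** Removal for uncontrolled pain is not an unrelated loss. It is caused by the quantity that the trial measures, and it ends the measurement. If BTX-A relieves pain, such removals should be rarer on BTX-A, so any rule that discards or lowers these women's scores acts mainly on the placebo arm and shrinks the measured benefit. If removals are more frequent on BTX-A, the same rule exaggerates the benefit.

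The listed methods do not treat these women alike. Complete case drops a woman if her later visits make her incomplete. Zero value enters her later pain as absent. Last value carries her final, probably high, score forward. Section 8.4, where it applies, gives her the maximum. Nothing says which result is primary for her, so the expansion-phase answer would depend on a choice made after the data are seen.

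**Working it through.** **The plan's own figure.** Section 7.1 assumes mean pain of 4.0 and 3.0, 80% power, a 0.05 significance level and a two-sample t-test. The planned 64 per arm corresponds to the table row with SD 2.0. A two-sided t-test calculation gives 63.8, so 64 per arm, with power 80.2%. The figure reproduces. The allowance for incomplete data is 134 − 128 = 6 women, or 6/134 = 4.5%.

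**Assumptions for the illustration.** The documents give neither removal rates nor pain levels at removal. Assumed here: true arm means 4.0 and 3.0 and SD 2.0, including the women removed; removed women at pain 8; a 0–10 scale (section 7.1 gives that range for the cited study's scale); and the rule applied to a removed woman's whole outcome. The last assumption makes the results upper bounds.

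**Formulas.** For an arm with true mean m and removal share p:

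- complete case: (m − 8p)/(1 − p)
- zero value: m − 8p
- worst score: m − 8p + 10p

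**Removal 10% on placebo, 5% on BTX-A.**

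- Complete case: (4 − 0.8)/0.90 = 3.56 and (3 − 0.4)/0.95 = 2.74; difference 0.82.
- Zero value: 3.2 and 2.6; difference 0.60.
- Worst score: 3.2 + 1.0 = 4.2 and 2.6 + 0.5 = 3.1; difference 1.10.
- Keeping the women at their own score of 8 returns 1.00.

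**Other assumed rates, same method (true difference 1.00).**

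| Placebo / BTX-A removal | Complete case | Zero value | Worst score |
|---|---|---|---|
| 5% / 2% | 0.89 | 0.76 | 1.06 |
| 10% / 5% | 0.82 | 0.60 | 1.10 |
| 10% / 2% | 0.66 | 0.36 | 1.16 |
| 5% / 5% | 1.05 | 1.00 | 1.00 |
| 0% / 5% | 1.26 | 1.40 | 0.90 |

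The direction depends on which arm has more removals.

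**Complete-case power at 10% / 5%.** Dropping scores of 8 also removes their variance. The remaining variance is (4 − p(8 − m)²)/(1 − p) − (complete-case mean − m)².

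- Placebo: 2.4/0.90 − 0.44² = 2.47, SD 1.57.
- BTX-A: 2.75/0.95 − 0.26² = 2.83, SD 1.68.
- Remaining numbers: 64 × 0.90 = 57.6 and 64 × 0.95 = 60.8.
- Standard error: √(2.47/57.6 + 2.83/60.8) = 0.299.
- Power (normal approximation): Φ(0.819/0.299 − 1.96) = 78%, against 81% by the same approximation with no removals.

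The same calculation gives about 76% at 5% / 2%.

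**The case against.** A reader might infer that women whose expander is removed drop out of the primary comparison, so that its answer describes only women who kept the expander. The documents do not support that. Each woman is scored at every appointment up to removal and possibly on the removal date. Those scores are retained, all randomized women are analysed, and results are tabulated by visit. Complete case is only one of several listed methods, and last value would keep a high final score.

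A reader might also infer that these women are necessarily treated as missing data. Section 8.1 lists post-operative pain and surgical site infection as expected adverse events of surgery, and has a condition that leads to surgery recorded as an adverse event if it meets the definition. Read with that, section 8.4 could give them the worst score. This defeats the claim that missing data is the only reading. It does not settle the matter, because section 8.4 is triggered by an adverse event with unblinding, never names removal, and is absent from section 7.

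A third tempting inference is a large loss of power, to about 60% at 10% / 5%. That figure keeps SD 2.0 after the extreme scores have been deleted, which contradicts the assumptions behind it.

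Two further objections stand. The sample size rests on pain during initial expansion, and another primary hypothesis concerns the immediate post-operative period; later removals touch neither much. Stopping at removal also fits a hypothesis about the period of expansion. The fault therefore lies in the handling of the event, not in where scoring stops.

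**Conclusion.** The concern holds in this limited form. Expander removal can be a consequence of the primary outcome, it ends scoring for any reason, and sections 7.2 and 8.4 could assign such a woman anything from the best pain score to the worst. Following the plan as written can bias the expansion-phase comparison in either direction.

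At the assumed 10% / 5% removal, a true difference of 1.0 is reported as 0.60, 0.82 or 1.10 according to the rule chosen. These are upper bounds on the distortion, since scores before removal are kept and the effect is greatest at late visits. Complete-case power changes little in that case (about 78%), so the issue is mainly bias and an open choice of rule. With no primary visit or summary fixed and no removal rates given, the actual size cannot be determined from the documents. The change should be made before unblinding; the gap does not invalidate the design.

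**What to change.** In sections 6 and 7.2:

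1. Separate planned exchange from unplanned removal of the expander.
2. For unplanned removal, make an NPIS and BREAST-Q at the decision or on the date of removal explicit, using the mail and telephone route that section 5.5 already provides.
3. Keep the woman in the primary expansion-phase comparison with her scores up to and including that one. She is neither dropped as incomplete nor given zero values.
4. Add a sensitivity analysis that gives removal for uncontrolled pain the worst rank in the Wilcoxon test already planned.
5. Report removals by arm and reason beside the pain result.
6. Reconcile section 8.4 with section 7.2 by stating whether the worst-score rule applies to expander removal.

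The cost is one extra form for a few women and some added wording. The worst-rank result is on the rank scale only and gives no difference in pain points.

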
1.5 Dose Rationale and Risk/Benefits

In our systematic review of the literature on the use of BTX-A with subpectoral breast implants²⁴, the dose of BTX-A administered to each patient in various studies ranged from 75 units to 200 units per breast. BTX-A was injected into the pectoralis major muscle alone in four studies, while in the study published by Layeeque et al., the toxin was injected in the pectoralis major muscle, serratus anterior and rectus abdominis muscle insertion of each breast. Richards et al. injected BTX-A in the pectoralis major muscle and subcutaneous tissues of the breast.

Based on these data, we concluded that an injection of 100 units of BTX-A per breast is a prudent choice. This dosage is also the standard dose used for several clinical indications, such as strabismus. In one study, 500 units of BTX-A were injected in the pectoralis major muscle of patients suffering of spastic shoulder pain after a cerebrovascular accident, and according to the authors, no important adverse event occurred.¹⁸

We have opted for an intra-operative injection rather than a pre-operative injection prior to surgery to minimize a theoretical risk of tumor seeding from percutaneous needle injection. **The BTX-A injection will be performed intra-operatively under general anesthesia, after all irrigations of the surgical site are completed, BUT prior to the placement of the tissue expander under the pectoralis major muscle to avoid any inadvertent puncture of the prosthetic device. BTX-A will be given only once during surgery and will not be repeated postoperatively.** The reason for giving the injection during the surgery is that it will allow the anti-nociceptive action of BTX-A to take effect immediately while the paralytic action will take about 7 to 10 days to take effect, thus coinciding with the start of tissue expansion. Furthermore, since the pectoralis major muscle is large and easily accessible, intra-muscular injection will be ascertained during surgery as it will be performed under direct visualization of the muscle. The clinical effects of a single injection of BTX-A usually lasts 3-4 months.²⁸ On average, the duration of tissue expansion usually ranges between 1 and 4 months. Therefore, our study design is based on a single intraoperative injection of BTX-A, and no repeat injection will be performed on patients enrolled in this study.

Safety, Risks and Adverse Effects:

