3.4 Primary Safety Endpoints

The primary safety endpoints of this study is the incidence of side effects attributable to the injection of BTX-A at doses of 100 units and 200 units, in women undergoing immediate post-mastectomy breast reconstruction with tissue expander(s).

Patients will be advised to inform the Principal Investigator and the study coordinator immediately if they develop any unusual symptoms (including difficulty with swallowing, speaking, or breathing), or if any existing symptom worsens. Patients will also be counseled that if loss of strength, muscle weakness, blurred vision, or drooping eyelids occur, they should avoid driving a car or engaging in other potentially hazardous activities.

At each follow-up visit, the study coordinator will question study subjects about occurrence of adverse events. All serious adverse experiences will be collected and reported. Local side effects of BTX-A injection include a flu-like syndrome that is generally short-lived, dysphagia, and xerostomia. Unintended weakness of the muscle injected or of nearby muscles could also be a negative effect. Other rare potential side effects include muscle soreness, rash, headaches, light-headedness, fever, chills, hypertension, diarrhea, abdominal pain, swallowing and breathing difficulties. Furthermore, the status of wound healing and tissue integrity will be performed at the first postoperative visit for all patients (i.e., at one to two weeks following surgery).

4 Subject Selection Enrollment and Withdrawal

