5.5 Subject Compliance Monitoring

To assure adherence to the one-time intraoperative study drug intervention, the study coordinator will review documentation of intraoperative medications. Monitoring adherence of timely questionnaire completion at each tissue expansion visit will also occur. For patients who will undergo tissue expansions at Mayo Clinic, the study coordinator will ensure that the questionnaires have been fully completed by the study participants before they leave the premises.

In some instances, study participants will not return to Mayo Clinic for each tissue expansion visit. The study coordinator will prepare a packet for these women that will include 7 questionnaires and 7 prepaid return envelopes by post. The study participants are to fill out and return one copy of the questionnaire at each tissue expansion visit performed at an outside institution. To maximize the response rate, we will use the methodology recommended by Dillman⁷³. If the questionnaire is not returned within one week after the planned tissue expansion visit, the study coordinator will contact the patient, and complete the questionnaire by phone. A telephone script will be used for this purpose. If the patient cannot be reached by phone, a reminder will be sent along with one additional copy of the questionnaire.

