- **Serious:** Serious problems or events that results in significant harm, (which may be physical, psychological, financial, social, economic, or legal) or increased risk for the subject or others

(including individuals who are not research subjects). These include: (1) death; (2) life threatening adverse experience; (3) hospitalization - inpatient, new, or prolonged; (4) disability/incapacity - persistent or significant; (5) birth defect/anomaly; (6) breach of confidentiality and (7) other problems, events, or new information (i.e. publications, DSMB reports, interim findings, product labeling change) that in the opinion of the local investigator may adversely affect the rights, safety, or welfare of the subjects or others, or substantially compromise the research data, **AND**

- Unanticipated: (i.e. unexpected) problems or events are those that are not already described as potential risks in the protocol, consent document, not listed in the Investigator's Brochure, or not part of an underlying disease. A problem or event is "unanticipated" when it was unforeseeable at the time of its occurrence. A problem or event is "unanticipated" when it occurs at an increased frequency or at an increased severity than expected, **AND**
- Related: A problem or event is "related" if it is possibly related to the research procedures.

Adverse Event Reporting Period

The study period during which adverse events must be reported is normally defined as the period from the initiation of any study procedures to the end of the study treatment follow-up. For this study, the study treatment follow-up is considered the four month postoperative period following study drug administration.

Preexisting Condition

A preexisting condition is one that is present at the start of the study. A preexisting condition should be recorded as an adverse event if the frequency, intensity, or the character of the condition worsens during the study period.

General Physical Examination Findings

At screening, any clinically significant abnormality should be recorded as a preexisting condition. At the end of the study, any new clinically significant findings/abnormalities that meet the definition of an adverse event must also be recorded and documented as an adverse event.

Post-study Adverse Event

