8.2 Recording of Adverse Events

At each contact with the subject, the investigator must seek information on adverse events by specific questioning and, as appropriate, by examination. Information on all adverse events should be recorded immediately in the source document, and also in the appropriate adverse event section of the case report form (CRF). All clearly related signs, symptoms, and abnormal diagnostic, laboratory or procedure results should be recorded in the source document.

All adverse events occurring during the study period must be recorded. The clinical course of each event should be followed until resolution, stabilization, or until it has been ultimately determined that the study treatment or participation is not the probable cause. Serious adverse events that are still ongoing at the end of the study period must be followed up, to determine the final outcome. Any serious adverse event that occurs after the study period and is considered to be at least possibly related to the study treatment or study participation should be recorded and reported immediately.

Adverse events will be monitored and recorded during the four month postoperative time period.

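### The protocol sets a four-month adverse-event period for every woman, but scheduled enquiry stops at expander removal or the last appointment before it, and no contact at month 4 is guaranteed

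*Combined protocol and SAP*

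**What the plan says.** **The window.** Section 8.1 (Adverse Event Reporting Period) states that "the study treatment follow-up is considered the four month postoperative period following study drug administration". Section 8.2 repeats it: "Adverse events will be monitored and recorded during the four month postoperative time period". Section 3.1 likewise plans four months of follow-up for each participant. The length fits the expected action of the drug in Section 1.5: "The clinical effects of a single injection of BTX-A usually lasts 3-4 months".

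**The scheduled enquiries.** Section 3.4 says: "At each follow-up visit, the study coordinator will question study subjects about occurrence of adverse events". The Table of Visits in Section 6 places this assessment at the first postoperative visit and at later plastic surgery or expansion visits, whose timing the surgeon decides. The end of study is the last plastic surgery appointment before the expander is taken out, "or the date of TE removal (whichever occurs last within the 4 month postoperative period".

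**Visits elsewhere.** Section 5.5 provides seven questionnaires and return envelopes: "The study participants are to fill out and return one copy of the questionnaire at each tissue expansion visit performed at an outside institution". The coordinator telephones if a form is not returned within a week. Section 9.3 adds a call when a returned form has gaps.

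**Other routes.** Section 8.2 requires specific questioning about adverse events at every contact. Section 3.4 asks women to report unusual symptoms at once. After the last scheduled visit, Section 8.1 (Post-study Adverse Event) asks them to report events that they or their physician think may be related to taking part.

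**The concern.** The primary safety endpoint (Sections 3.4 and 7.1) is the incidence of side effects attributable to the injection. An incidence needs a defined observation period over which everyone is asked. Here the period is fixed at four months, but the last planned enquiry depends on when the expander comes out and when appointments happen to fall, both of which are settled after randomisation.

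Two consequences follow. First, a woman whose expander is lost to a complication leaves scheduled enquiry early, although she is one whose later course matters for safety. Second, Section 7.2 suggests that the "use of BTX-A may increase the rate of tissue expansion, which may lead to fewer postoperative tissue expansion visits". If so, the intensity of enquiry could differ by arm. Section 8.5 also makes some single events, such as upper limb weakness or blurred vision, grounds for stopping unless shown to be unrelated, so it matters that events are found.

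**Working it through.** The plan gives no figure to reproduce on this point. The check sets the passages side by side.

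1. **Required period.** Four months from injection, for everyone (Sections 3.1, 8.1, 8.2).
2. **Last scheduled enquiry.** At latest, expander removal if that falls within four months. If the expander is still in place, it is whichever appointment falls last before month 4 (Section 6). Nothing here rests on the End of Study row showing no activity, which may be a formatting effect. An enquiry in that row would still fall no later than removal.
3. **Gap.** If removal occurs at month *m*, the time with no scheduled enquiry is 4 − *m* months. For example, *m* = 3 leaves 1 month and *m* = 2 leaves 2 months. With a drug effect of 3 to 4 months (Section 1.5), removal at month 2 leaves 3 − 2 = 1 to 4 − 2 = 2 months of expected effect with no scheduled enquiry. These values of *m* are assumptions, because no removal times are given. The 1 to 4 months in Section 1.5 is the duration of expansion, and no passage says that the expander is removed when expansion finishes.
4. **Early removal does occur in the plan's own terms.** Section 3.3 counts removal for any cause, with infection and uncontrolled pain as examples, as reconstructive failure. Such a removal also ends the visit schedule.
5. **What remains after the last visit.** The rule of questioning at each contact (Section 8.2) governs contacts that take place and creates none. The post-study rule in Section 8.1 is started by the woman and limited to events thought to be related.
6. **Visits elsewhere.** The packet is described as questionnaires and envelopes. Calls follow non-return (Section 5.5) or missing items (Section 9.3). A woman who returns every form complete triggers neither, so no contact is planned at which the Section 8.2 rule would apply to those visits. Section 5.5 says only that this happens in some instances.

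**Can a size be attached to a difference between arms?** Only by assumption. Suppose both arms have the same true four-month risk *R*, the hazard is constant, and nothing is reported after the last enquiry at month *m*. The observed risk is then 1 − (1 − *R*)^(*m*/4). Taking *R* = 10%:

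| Last enquiry, placebo / BTX-A (months) | Observed risk, placebo / BTX-A | Ratio |
|---|---|---|
| 4 / 4 | 10.0% / 10.0% | 1.00 |
| 3 / 2.5 | 7.6% / 6.4% | 0.84 |
| 4 / 3 | 10.0% / 7.6% | 0.76 |
| 4 / 2 | 10.0% / 5.1% | 0.51 |

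The result runs from no distortion to about a halving, depending entirely on inputs that the documents do not supply. None of these ratios is an estimate for this trial.

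**The case against.** The strongest reply is that ascertainment does not rest on the visit table alone. Section 8.2 requires questioning at each contact, telephone calls included, and women are told to report unusual symptoms immediately. Much of the relevant risk also comes early. Section 1.3 puts the onset of muscle effect within days to a week and its peak within two weeks, and Section 1.5 describes distant spread as arising hours to weeks after injection. The visit at one to two weeks covers much of that period in both arms and includes a wound check. This stands, and it limits how much could be missed. It does not supply a scheduled contact at month 4.

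Four stronger readings are tempting and should not be drawn:

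- *Adverse events are sought only at clinic visits.* The each-contact rule and self-report contradict this. What is tied to visits is scheduled enquiry.
- *Safety follow-up is shorter on BTX-A.* Faster expansion is a hypothesis, and the schedule ends at removal or the last appointment, not at the end of expansion. Appointments while waiting for exchange also carry an adverse-event assessment. The most that Section 7.2 supports is possibly fewer visits, and fewer enquiries need not lower the proportion with an event, since each can cover the time since the previous one.
- *Women expanded elsewhere go mostly unasked.* Their number is not given, and they may miss only some visits at the study clinic.
- *The infection stopping rule in Section 8.5 is materially weakened.* Infection may cluster early, infection leading to removal is also captured as reconstructive failure, and no passage says that infection rates come from coordinator questioning alone.

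**Conclusion.** The concern holds as a mismatch between the stated safety window and the schedule meant to fill it. Sections 3.1, 8.1 and 8.2 promise four months. Section 6 does not guarantee it, and Section 5.5 mentions no adverse-event item for visits elsewhere. Followed as written, the plan leaves the later part of the window to self-report for any woman whose expander is removed early, and to chance appointment timing for the others. This conclusion rests on the text alone.

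Less frequent enquiry in the BTX-A arm is conditional on the sponsor's own hypothesis of fewer visits, and its size cannot be derived from the documents. The matter deserves correction because it touches the primary safety endpoint and because enquiries not made cannot be fully recovered at analysis. It does not show that the safety comparison is biased.

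**What to change.** 1. In the Section 6 table, separate the end of outcome assessment from the end of safety follow-up, so that it agrees with Sections 3.1, 8.1 and 8.2.
2. Add one scripted coordinator telephone call about adverse events at month 4 for every randomised woman, whatever the date of expander removal and wherever she was expanded.
3. Add an adverse-event and infection checklist page to each mailed questionnaire, with non-return and gaps handled by the telephone follow-up already in Sections 5.5 and 9.3.
4. In Section 7.2, state that adverse-event incidence is reported by arm over the fixed 0-4 month window. Record the date of expander removal so that events after a second operation can be identified.

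With a month-4 contact for everyone, active enquiry covers the full window in both arms, and in the illustration above equal true risks give a ratio of 1.00 whatever the removal times.

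Cost: at most 134 short calls by the existing coordinator, one extra page per mailed questionnaire (seven per packet), and a protocol amendment. No treatment or clinical procedure changes.
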